## **6 TRIAL TREATMENT**

GEN3014 and daratumumab combined with hyaluronidase-fihj are the IMP intended to be administered to a trial subject according to the trial protocol. See Section 10.15.3 for a comprehensive list of all IMPs and AMPs used in this trial (and their EU authorization status).

### **6.1 Trial Treatment(s) Administered**

#### **6.1.1 GEN3014 IV**

GEN3014 will be administered as an IV infusion, by qualified site personnel. Each subject's dose will be calculated based on the subject's weight rounded to the nearest kilogram, but does not need to be recalculated for weight changes that are <10% from baseline. Refer to Section 6.2 for pre-infusion medication and post-infusion medication requirements. Detailed dose modification guidance is provided in Section 6.6. Refer to Section 6.7 for information regarding concomitant therapy. GEN3014 treatment should be continued until 1 or more of the discontinuation criteria in Section 7 are met.

Each infusion is estimated to last between 1 and 8 hours.

The first dose of GEN3014 should be split into 2 consecutive days (ie, C1D1 and C1D2).

Please refer to the latest version of the IMP Manual for detailed instructions. For country-specific information, see Section 10.15.1.

#### **6.1.2 Daratumumab SC**

Daratumumab (1800 mg) will be administered by SC injection by manual push over approximately 3 to 5 minutes in the abdominal subcutaneous tissues in left/right locations, alternating between individual doses. The volume of the SC solution will be 15 mL for the 1800 mg dose. The dose of daratumumab will remain constant throughout the trial.

Detailed dose modification guidance is provided in Section 6.6. Refer to Section 6.7 for information regarding concomitant therapy. Daratumumab SC treatment should be continued until 1 or more of the discontinuation criteria in Section 7 are met.

Detailed instructions will be provided in the IMP Manual.

### **6.1.3 Physical Description of Trial Drugs**

#### **6.1.3.1 GEN3014**

GEN3014 is formulated as a liquid, 20 mg/mL, clear to slight opalescent, colorless to slight yellow solution. It will be manufactured and provided under the responsibility of the sponsor.

Refer to the GEN3014 IB for a list of excipients.

#### **6.1.3.2 Daratumumab SC**

Daratumumab SC (daratumumab and hyaluronidase-fihj) injection is a sterile, preservative-free, colorless to yellow, and clear to opalescent solution for subcutaneous use supplied as individually packaged single-dose vials providing 1800 mg of daratumumab and 30,000 units of hyaluronidase per 15 mL.

Refer to the daratumumab IB for a list of excipients.

## **6.1.4 Packaging of Trial Drugs**

### **6.1.4.1 GEN3014**

GEN3014 will be packaged with 1 vial per box, with an aluminum cap on the vial.

### **6.1.4.2 Daratumumab SC**

Daratumumab SC will be packed with 1 vial per box.

## **6.1.5 Labeling**

Trial drug labels will contain information to meet the applicable regulatory requirements. For further details see the latest version of the IMP Manual.

## **6.1.6 Treatment Schedule**

### **6.1.6.1 GEN3014 Administration Schedule for Expansion Part A (GEN3014 Single Cohorts) and Expansion Part B (Randomized H2H)**

GEN3014 will be administered as an IV infusion at the RP2D (ie, 16 mg/kg) in cycles of 4 weeks, ie, 28 days, as follows:

- Cycle 1 (Q1W) on Days 1, 2\*, 8, 15, and 22. Note: \*The first dose of GEN3014 will be split into 2 consecutive days (ie, C1D1 and C1D2).
- Cycle 2 (Q1W) on Days 1, 8, 15, and 22
- Cycle 3-6 (Q2W) on Days 1 and 15
- Cycle 7 and beyond (Q4W) on Day 1

Dosing days may be adjusted to accommodate the schedule of the site or the subject. Changes to within-cycle dosing should not affect Day 1 of the next cycle.

### **6.1.6.2 Post-infusion Monitoring After GEN3014 Administration for Expansion Part A (GEN3014 Single Cohorts) and Expansion Part B (Randomized H2H)**

- During treatment Cycle 1 in the Expansion Part A (GEN3014 Single Cohorts) and Expansion Part B (Randomized H2H), all subjects are required to remain in the clinic after each GEN3014 infusion for at least 4 hours where they will be observed closely. Vital signs need to be monitored as per Section 8.3.3.
- Beyond observation for AEs, vital signs will be measured and blood sampling for laboratory parameters, cytokines, PK and pharmacodynamic measurements will be performed.
- If clinically indicated, observation of up to 24 hours postdose during Cycle 1 is acceptable at the discretion of the investigator.
- If a subject has an IRR of  $\geq$  grade 3 during any infusion, the subject will be required to stay overnight following the infusion. If a subject is hospitalized for prolonged monitoring post-infusion, the hospitalization should not be reported as SAEs.

### **6.1.6.3 Daratumumab SC Administration Schedule for Expansion Part B (Randomized H2H)**

Daratumumab (1800 mg) will be administered by SC injection by manual push over approximately 3 to 5 minutes in the abdominal subcutaneous tissues in left/right locations,

alternating between individual doses. The volume of the SC solution will be 15 mL for the 1800 mg dose. The dose of daratumumab will remain constant throughout the study.

Refer to the IMP Manual for additional guidance on administration of daratumumab SC.

**Table 6-1 Daratumumab SC Dosing Schedule, 4-Week Cycle Dosing Regimens**

Weeks	Schedule
Weeks 1 to 8	weekly (total of 8 doses)
Weeks 9 to 24 a	every 2 weeks (total of 8 doses)
Week 25 onwards until disease progression b	every 4 weeks

a First dose of the every-2-week dosing schedule is given at Week 9.

b First dose of the every-4-week dosing schedule is given at Week 25.

#### **6.1.6.4 Post-injection Monitoring After Daratumumab Administration for Expansion Part B (Randomized H2H)**

See Section 6.2.5.

### **6.1.7 Technical Complaint Handling**

A technical complaint is defined as any suspicion of a product defect related to manufacturing, labeling, or packaging, ie, any dissatisfaction relative to the identity, quality, durability, or reliability of a product, including its labeling or package integrity. A technical complaint may have an impact on the safety and efficacy of the product. Timely, accurate, and complete reporting and analysis of technical complaint information from trials are crucial for the protection of subjects, investigators, and the sponsor, and are mandated by regulatory agencies worldwide. The sponsor has established procedures in conformity with regulatory requirements worldwide to ensure appropriate reporting of technical complaint information; all trials conducted by the sponsor or its affiliates will be conducted in accordance with those procedures. Refer to the IMP Manual for additional details.

#### **6.1.7.1 Procedures**

All initial technical complaints must be reported to the sponsor by the trial-site personnel within 24 hours after being made aware of the event.

If the defect is combined with an SAE, the trial-site personnel must report the technical complaint to the sponsor according to the SAE reporting timelines (refer to Section 8.4.3.1, Serious Adverse Events). A sample of the suspected product should be maintained for further investigation if requested by the sponsor.

#### **6.1.7.2 Contacting Sponsor Regarding Technical Complaints**

The names (and corresponding telephone numbers) of the individuals who should be contacted regarding technical complaint issues are listed on the Sponsor Contact page (provided separately from the protocol).

## **6.2 Pre-administration and Post-administration Prophylaxis**

### **6.2.1 Premedication Prior to GEN3014 and Daratumumab SC Administration**

The purpose of premedication is to reduce the risk of IRRs and sARRs. It is mandatory to premedicate subjects with corticosteroids, antihistamines, and antipyretics, before each

GEN3014 and daratumumab SC administration ([Table 6-2](#)). Premedication specified should be administered 1 to 3 hours prior to GEN3014 and daratumumab SC administration:

- Methylprednisolone 100 mg, or equivalent, administered IV in accordance with the recommended dose for the management of infusion related reactions ([Roselló et al., 2017](#)). Only intermediate-acting and long-acting steroids are allowed (please refer to [Table 6-3](#) for conversion table).
- Antipyretics (paracetamol [acetaminophen]) 650 to 1000 mg PO in accordance with the recommended dose for the management of infusion related reactions ([Roselló et al., 2017](#)).
- An antihistamine: Diphenhydramine 25 to 50 mg IV or PO, or equivalent in accordance with the recommended dose for the management of infusion related reactions ([Roselló et al., 2017](#)).
- Predose administration of a leukotriene inhibitor (montelukast 10 mg PO, or equivalent) is optional on Cycle 1 Day 1.
- If there is no IRR during the first treatment cycle, the dose of corticosteroid may be reduced for subsequent cycles, ie, methylprednisolone at 60 mg IV or PO.

**Table 6-2 Premedication Schedule**

Pre-Infusion Medication	First Cycle	Subsequent Infusions
Methylprednisolone 	100 mg IV	60 mg IV or PO
Paracetamol (acetaminophen)	650 to 1000 mg PO	650 to 1000 mg PO
Diphenhydramine 	25 to 50 mg IV or PO	25 to 50 mg IV or PO

IV=intravenous; PO=per os (oral).

1. Or equivalent dose of an intermediate-acting or long-acting corticosteroid.

2. Or alternative antihistamine at a proper dose.

**Table 6-3 Corticosteroid Dose Equivalents**

Steroid	Approximate Equivalent Dose	Duration
Methylprednisolone	100 mg	Intermediate-acting
Betamethasone	20 mg	Long-acting
Dexamethasone	20 mg	Long-acting
Triamcinolone	100 mg	Intermediate-acting
Prednisone	125 mg	Intermediate-acting
Prednisolone	125 mg	Intermediate-acting

### **6.2.2 Post-GEN3014 Infusion and Post-Daratumumab SC Medication**

For subjects receiving GEN3014 IV in all disease cohorts or daratumumab SC in the Expansion Part B, administer post-administration medication to reduce the risk of delayed IRRs or sARRs as follows:

Administer methylprednisolone 20 mg (or an equivalent dose of an intermediate- or long-acting corticosteroid) orally for 2 days starting the day after the administration of GEN3014 IV or daratumumab SC. If the subject does not experience a major IRR or sARR after the first 3 doses of GEN3014 IV or daratumumab SC, consider discontinuing the administration of corticosteroids (excluding any background regimen-specific corticosteroid).

For subjects with a higher risk of respiratory complications (eg, subjects with mild asthma or subjects with COPD who have an FEV1 <80% at Screening or developed FEV1 <80% during the study without any medical history), the following post-treatment medications should be considered:

- Antihistamine (diphenhydramine or equivalent)
- Leukotriene inhibitor (montelukast or equivalent)
- Short-acting  $\beta_2$  adrenergic receptor agonist such as salbutamol aerosol
- Control medications for lung disease (eg, inhaled corticosteroids  $\pm$  long-acting  $\beta_2$  adrenergic receptor agonists for subjects with asthma; long-acting bronchodilators such as tiotropium or salmeterol  $\pm$  inhaled corticosteroids for subjects with COPD)

In addition, these at-risk subjects may be hospitalized for close monitoring at the investigator's discretion. If subjects are hospitalized, then an improvement in FEV1 should be performed and documented prior to discharge. If these subjects are not hospitalized, then a follow-up telephone call should be made to monitor their condition within 48 hours after all administrations. If the subject has not experienced a significant medical event but is hospitalized overnight only for observation, then the hospitalization should not be reported as an SAE. Investigators may prescribe bronchodilators, H1-antihistamines, and corticosteroids that are deemed necessary to provide adequate supportive care in the event a bronchospasm occurs after subjects are released from the hospital/clinic. If an at-risk subject experiences no major IRRs or sARRs, then these post-administration medications may be waived after 4 doses at the investigator's discretion.

Any post-administration medication will be administered after the administration has completed.

### **6.2.3 Management of GEN3014 Infusion-Related Reactions**

Subjects should be carefully observed during GEN3014 infusions. Trained trial staff should be prepared to intervene in case of any infusion related reactions occurring, with resources necessary for resuscitation. Interrupt GEN3014 infusion for IRRs of any severity and institute medical management/supportive treatment as needed:

- For grade 1 or 2 IRRs, stop the infusion immediately and treat the subject; once reaction symptoms resolve, resume the infusion at no more than half the rate at which the IRR occurred. If the subject does not experience any further IRR symptoms, infusion rate escalation may resume at increments and intervals as clinically appropriate.
- For grade 3 IRRs, stop the infusion immediately and treat the subject; once reaction symptoms resolve, resume the infusion at no more than half the rate at which the IRR occurred. If the subject does not experience any further IRR symptoms, infusion rate

escalation may resume at increments and intervals as clinically appropriate. If, after resumption of the infusion, symptoms return (irrespective of grade), permanently discontinue administration of GEN3014 and manage the IRR symptoms accordingly.

- For a grade 4 (life-threatening) IRR, permanently discontinue administration of GEN3014 and institute appropriate emergency care.

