## 6.6 Dose Modifications

### 6.6.1 Dose-Limiting Toxicity (Dose Escalation)

The DLT Evaluation Period is defined as the first 28 days of GEN3014 treatment (ie, Cycle 1). Toxicities will be graded for severity according to the National Cancer Institute Common Terminology Criteria for Adverse Events (NCI-CTCAE), v5.0, with the exception of TLS (see Section 10.3.7).

The occurrence of any of the toxicities outlined in this section will be considered a DLT.

- All Grade 5 toxicities
- Hematological toxicities listed below:
  - Grade 4 thrombocytopenia (platelet count  $<25.0 \times 10^9/L$  [ $<25,000/\mu L$ ]) lasting  $>7$  consecutive days not attributable to the underlying disease.
  - Grade 4 neutropenia (neutrophil count  $<0.5 \times 10^9$  cells/L [ $<500/\mu L$ ]) lasting  $>7$  consecutive days not attributable to the underlying disease.
  - Grade 3 and grade 4 febrile neutropenia (neutrophil count  $<1.0 \times 10^9$  cells/L with a single temperature of  $>38.3^\circ C$  [ $100.9^\circ F$ ] or with a sustained temperature of  $\geq 38^\circ C$  [ $\geq 100.4^\circ F$ ] for more than 1 hour) lasting  $>2$  days.
  - Grade 3 and grade 4 hemorrhage associated with thrombocytopenia of  $\geq$  grade 3 requiring platelet transfusion.
  - Grade 4 anemia
- Note: Since bone marrow aplasia is an expected consequence of AML therapies, only persistent pancytopenia lasting  $\geq 14$  days and not related to leukemia infiltration will be considered as a DLT for the R/R AML Cohort. Bone marrow evaluation may be required to determine if marrow aplasia is due to leukemia.
- Non-hematological toxicities:
  - All non-hematological toxicities of grade  $\geq 3$  (severe or life-threatening), **excluding** the following:
    - a. Grade 3 fever ( $>40.0^\circ C$  [ $>104.0^\circ F$ ]) for  $\leq 24$  hours
    - b. Grade 3 hypotension (medical intervention indicated; hospitalization indicated) resolving in  $\leq 24$  hours
    - c. Laboratory values out of normal range that do not have any clinical consequence, are clinically transient in nature and that resolve in  $\leq 3$  days (including electrolyte abnormalities that respond to medical intervention)
    - d. Grade 3 AST and/or grade 3 ALT returning to grade 1 or baseline in  $\leq 7$  days
    - e. Grade 3 nausea that responds to adequate antiemetic treatment in  $\leq 3$  days
    - f. Grade 3 vomiting that responds to adequate antiemetic treatment in  $\leq 3$  days

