#### **6.6.2 GEN3014 Dose Modification Guidance and Stopping Criteria (Dose Escalation and Expansion Part A)**

- No dose modification (increase or decrease) of GEN3014 will be permitted for this trial.
- If a subject experiences a DLT, the subject may continue treatment with GEN3014, if the toxicity recovers to  $\leq$  grade 2 or baseline within 4 weeks from occurrence of the DLT. Continued administration of GEN3014 must be agreed to between the sponsor and the investigator based on a thorough assessment of the event, the duration of the event, and benefit-risk for the subject. In the event a subject experiences a second episode of a DLT with GEN3014, the treatment will be permanently discontinued. Treatment with GEN3014 will be discontinued in the event the DLT is not resolved within 4 weeks.
- If a subject experiences toxicity that would have qualified as a DLT but the event occurs after the DLT evaluation period, the subject's benefit-risk must be thoroughly assessed. Continued treatment with GEN3014 must be agreed between the sponsor and the investigator.
- For the subject who receives treatment beyond the DLT evaluation period, all corresponding AEs that would have met the DLT criteria will be considered for the purpose of determining the RP2D and/or MTD (if reached). For the declaration of the RP2D from the Dose Escalation for further development of GEN3014 in the Expansion, the totality of the data including safety, PK, pharmacodynamics, and preliminary efficacy will be evaluated.
- During the trial, a planned dose of GEN3014 can be postponed for up to 4 weeks due to an AE whether it is considered drug-related or not.

- In case of dose delay of more than 4 weeks from the last trial drug administration due to toxicity, GEN3014 should be discontinued, unless resuming administration of GEN3014 is agreed between the sponsor and the investigator.
- During the trial, the GEN3014 dose can be held for the following laboratory results:
  - a. If platelet count is  $<50 \times 10^9/L$ , hold dose until platelet count is  $\geq 50 \times 10^9/L$ .
  - b. If febrile neutropenia is  $<0.5 \times 10^9/L$ , hold dose until neutrophil count is  $\geq 0.5 \times 10^9/L$ .
  - c. If hemoglobin is  $<8$  g/dL ( $<8$  g/L or  $<5$  mmol/L), hold dose until hemoglobin is  $\geq 8$  g/mL ( $\geq 8$  g/L or  $\geq 5$  mmol/L).

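### Section 6.2.3 ends GEN3014 permanently at a grade 4 infusion reaction, but 6.6.2 allows agreed continuation after a first DLT, which by 6.6.1 includes that same reaction

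*Protocol*

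**What the plan says.** Four parts of the protocol bear on what happens after a grade 4 IRR to GEN3014.

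- **Section 6.2.3** (IRR management): "For a grade 4 (life-threatening) IRR, permanently discontinue administration of GEN3014 and institute appropriate emergency care". It gives no exception and no route by agreement.
- **Section 6.6.1** (DLT definition, Dose Escalation): "The DLT Evaluation Period is defined as the first 28 days of GEN3014 treatment". Any toxicity on its list is a DLT, and grade 4 IRR is on the list by name.
- **Section 6.6.2** (Dose Escalation and Expansion Part A): "If a subject experiences a DLT, the subject may continue treatment with GEN3014, if the toxicity recovers to" grade 2 or lower, or baseline, within 4 weeks. The condition is that "Continued administration of GEN3014 must be agreed to between the sponsor and the investigator based on a thorough assessment of the event". Its own permanent stop comes one event later: "In the event a subject experiences a second episode of a DLT with GEN3014, the treatment will be permanently discontinued". Treatment also stops if the DLT has not resolved within 4 weeks. The next bullet covers "toxicity that would have qualified as a DLT but the event occurs after the DLT evaluation period" and leaves continuation to the same two parties.
- **Section 7.1** (discontinuation of trial treatment): the adverse-event entry refers to 6.6.2 for GEN3014 and to 6.6.3 for daratumumab SC. It does not mention 6.2.3.

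**The concern.** One named event falls under two rules with different answers. A site that opens 6.2.3 finds that treatment is over. A site that classes the event as a DLT and follows 6.6.2, where 7.1 sends it, finds that treatment may go on if the sponsor agrees.

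The event is not peripheral. IRRs are the adverse event of special interest for GEN3014 (Section 8.4.1.1). Section 2.3 expects them with this drug and notes that, with anti-CD38 antibodies, they fall mostly in the first cycle. That cycle is also the DLT period. At stake is re-exposure of a subject who has already had a life-threatening reaction, under a provision that another section of the same protocol rules out.

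**Working it through.** No formula applies. The check sets the sections side by side for one case: a subject in Dose Escalation has a grade 4 IRR in Cycle 1 and recovers to grade 2 or lower, or baseline, within 4 weeks.

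| Step | Section | Result for this subject |
|---|---|---|
| 1 | 6.2.3 | Permanent stop at the first event |
| 2 | 6.6.1 | The event is a DLT, by name |
| 3 | 6.6.2, DLT bullet | May continue if sponsor and investigator agree; no IRR exception, no reference to 6.2.3 |
| 4 | 6.6.2, later stops | Not triggered: no second DLT episode, and resolved within 4 weeks |
| 5 | 7.1 | GEN3014 adverse-event stopping is referred to 6.6.2 |
| 6 | 6.1.1 | Treatment runs until a Section 7 criterion is met, which for adverse events leads back to 6.6.2 |

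**Could step 1 mean only that day's infusion?** No. The grade 1 to 3 bullets in 6.2.3 speak of stopping the infusion and then resuming it. The grade 4 bullet uses different words and allows no resumption.

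**Is precedence stated anywhere?** Section 2.3 says that IRR management is found in Section 6.2, but does not say that it overrides 6.6.2. Section 10.15.1 (Czech Republic) says that 6.2.3 must be followed and mentions interruption, supportive care and a lower infusion rate. That list is introduced as inclusive, so the absence of permanent discontinuation from it proves nothing either way. No other text settles the order.

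**Where does the conflict sit?** Section 4.1.1.1 puts Cycle 1 infusions on Days 1, 2, 8, 15 and 22, which is 5 infusion days. MM-DL1 adds Day 9, giving 5 + 1 = 6. All fall within the 28-day DLT period, so every Cycle 1 infusion in Dose Escalation lies inside the window. This counts opportunities, not risk.

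**How many subjects could still meet it?** Section 4.3.2 reports that 16 mg/kg has been selected as the recommended phase 2 dose on the Dose Escalation data. The remaining escalation exposure may therefore be mainly R/R AML, capped at 18 subjects by Section 4.1.2.1. The documents do not say how many are still to be dosed.

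**After Cycle 1.** The second 6.6.2 bullet leaves a grade 4 IRR to sponsor-investigator agreement as well, where 6.2.3 again leaves no choice.

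**The case against.** The best case for the plan is that both sections can be obeyed at once. Section 6.2.3 is a specific order and 6.6.2 is a general permission, and on an ordinary reading a permission does not cancel an order in the same protocol. Re-challenge needs the sponsor and the investigator both to overlook or override 6.2.3. Section 7.1 also lists sponsor decision and an open category, so a stop under 6.2.3 has somewhere to be recorded. Section 10.1.1 holds investigators to the whole protocol. Sections 4.1.1.1 and 6.1.1 send sites to the IMP Manual, which is not among the documents and might settle the matter.

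Much of this stands, and it is why the point is minor. It does not remove the contradiction. Section 6.6.2 is itself specific to DLTs, grade 4 IRR is a DLT by name, and 7.1 identifies 6.6.2 as the GEN3014 rule. Permission to re-challenge is exactly what 6.2.3 withholds.

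A reader might go further and infer that the second stop in 6.2.3 is contradicted too. After a grade 3 IRR it says "If, after resumption of the infusion, symptoms return (irrespective of grade), permanently discontinue administration of GEN3014 and manage the IRR symptoms accordingly". The argument would be that 6.6.1 counts "All non-hematological toxicities of grade" 3 or higher as DLTs and does not list IRR among the exclusions. The documents leave this only arguable. Section 6.6.1 names IRR at grade 4 alone, which would be redundant if the general bullet already covered it. Section 4.1.1 lists IRR of grade 3 or higher and a DLT as separate triggers for enlarging a single-subject dose level. Section 10.3.7 handles tumor lysis syndrome in parallel: grades 1 to 3 go to dose-modification guidance and only grade 4 is called a DLT. The returning symptoms may also be of any grade.

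A reader might also extend the point to Part B or to daratumumab SC. The restart rule in 6.6.3.1.1 is a general dose-delay rule and does not name the reaction as 6.6.1 does. No daratumumab conflict is shown here.

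**Conclusion.** Wrong as written: an internal contradiction in a safety stopping rule, of minor severity. For a first grade 4 IRR that recovers in time, 6.2.3 requires a permanent stop and 6.6.2 permits agreed continuation. The two rules differ by one event, subject to the 4-week resolution condition in 6.6.2.

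The protocol does not direct anyone to re-challenge. The risk is confined to a re-challenge that the sponsor has agreed to, mainly in Cycle 1 of Dose Escalation. The direct conflict is not claimed for Part A: 6.6.2 covers it by title, but the DLT period is defined only for Dose Escalation.

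It would also be wrong to infer an effect on the statistics. A grade 4 IRR counts as a DLT whichever section governs later treatment, so DLT counts, the modified BOIN decisions and the efficacy analyses do not change.

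The conclusion rests on the protocol text alone and assumes that no unseen document, such as the IMP Manual, fixes precedence.

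**What to change.** 1. In the 6.6.2 bullet on continuing after a DLT, and in the bullet on DLT-type toxicity after the DLT period, add: *except grade 4 IRR, which requires permanent discontinuation per Section 6.2.3*.
2. In the adverse-event entry of 7.1, add Section 6.2.3 to the GEN3014 stopping-rule reference.

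Optionally, 6.6.2 could also point to the 6.2.3 rule on symptoms returning after a grade 3 IRR. That would be clarification rather than repair. Edits to 6.2.4 references or to 6.6.3.1.1 are not needed for this point.

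The cost is wording in two sections at the next amendment, with no change to design, sample size or analysis.
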